2.1 Investigational product(s)

Powered muscle stimulator/ GMORE

GM300E

2.2 Animal and preclinical study data

Not applicable

2.4 Risks / benefits Assessment

1. In our preliminary study, relative high protein intake (1.2g/kg/day) for less than one month had no significant impact on renal function. We will follow serum creatinine level at least twice per week for monitoring.

2.5 Regulatory

This study will be conducted in compliance with the protocol approved by the Institutional Review Board, and according to Good Clinical Practice standards. No deviation from the protocol will be implemented without the prior review and approval of the IRB except where

it may be necessary to eliminate an immediate hazard to a research subject. In such case, the deviation will be reported to the IRB as soon as possible.

3. Objectives and Endpoints

3.1 Study Objectives:

3.1.1 Primary objective:

To evaluate the benefit of high protein supplementation and core muscle rehabilitation and trunk NMES intervention in weaning from ventilator

3.1.2 Secondary objectives:

The impact of renal function and digestion status after high protein intake
The benefit in nutrition status and diaphragm weakness and the correlation to weaning status

3.1.3 Other exploratory objectives (if any):

1.2 Study endpoints:

3.2.1 Primary endpoint:

Weaning rate

(weaning success defined as weaning from ventilator for 5 consecutive days)

3.2.2 Secondary endpoints:

In hospital mortality, Length of mechanical ventilator usage,
Length of ICU stay and total length of hospitalization,
Serum albumin level improvement, Creatinine clearance rate

3.2.3 Other exploratory endpoints (if any):

4. Study Design

4.1 Overall Design

Research principles and methods

Patients

Patients (age \geq 20 years old) on mechanical ventilator for more than 21 days were recruited from

the respiratory care center (RCC). of Chang Gung Memorial Hospital in Taiwan.

The **inclusion criteria** were as follows:

1. age \geq 20 year old
2. using mechanical ventilator for more than 21 days (including patients under tracheostomy or endotracheal tube)
3. stable clinical condition, without using inotropic agent
4. maximal inspiratory pressure (MIP) $< 30\text{mmHg}$
5. under enteral nutrition (EN) via NG tube.

The **exclusion criteria** were as follows:

1. Acute infection and sepsis (fever up to 38.5 degree)
2. Severe neuromuscular disease, or uncontrolled epilepsy
3. Bony fracture or DVT history
4. Wound over the abdomen
5. Congestive heart failure with EF $< 40\%$ or using pacemaker
6. $\text{BMI} > 35 \text{ kg/M}^2$, or severe edema
7. Patients with hepatic failure, rapid progressed malignancy, or pregnancy were also excluded.
8. Under parenteral nutrition (PN)
9. Use pacemaker

Patient's identification will be recorded as a study code, which will not be mentioned in the publication.

[figure not shown]
Study Protocol

Patients will be randomly assigned into four groups: (1) Usual care (UC), (2) UC + high protein diet (HP), (3) UC + HP + core muscle rehabilitation, (4) UC + HP + core muscle rehabilitation + neuromuscular electric stimulation (NMES). Ten patients will be assigned to UC group. Thirty patients will be included in another 3 group. Before subject recruitment, sequential sealed envelopes were prepared by an independent investigator ([name]), with one chosen randomly by another investigator for each subject. The subjects were then assigned to each group according to the label in the envelope. The total daily caloric intake is based on the suggestion of nutritionist. The HP groups will maintain unchanged total daily caloric intake and increasing protein content to 1.5g/kg/day. The specific formulas were chosen for their different energy and

protein requirement (mainly Nutri-Aid , or NU-PEP HN , according to patients' digestion, and may add Whey-Aid if necessary (above formula are available in CGMH currently)). We will maintain the nutrition strategies for 21 days according to patients' weaning condition. Protein provision was not reduced in case of renal failure. Core muscle rehabilitation is sitting on bedside with or without aids, for 30 minutes, twice per day, 5 days per week, for 3 weeks. NMES was applied for 30 min, twice per day, 5 days per week, for 3 weeks via surface rectangular electrodes. Electrodes were placed on back designed to activate latissimus dorsi and abdominal wall designed to activate the transversus abdominis and internal and external oblique muscles as previously McCaughey et al described ³⁷. Electrical muscle stimulation was performed by using a commercial stimulator (GEMORE, GM300E, Taipei, Taiwan) with biphasic waves at a simulation frequency of 30 Hz and pulse width of 400s, cycling 2s on and 4s off. Electrical muscle stimulation intensity was gradually increased until a visible muscle contraction was observed (median 60 mA [range 50–65 mA]).

The age, gender, smoking history, diagnosis, length of mechanical ventilator use, APACHE II will be recorded. The pulmonary performance, including tidal volume, maximal inspiratory pressure (MIP), cough function, peak inspiratory pressure (PIP), positive end-expiratory pressure (PEEP), lung compliance, airway resistance, blood gas analysis, Barthel index, serum albumin, creatinine, electrolytes will record before, during (twice per week) and after intervention. We also follow the outcome of hospitalization, including the weaning rate, mortality, length of mechanical ventilator use, length of ICU stay and total length of hospitalization. We will further evaluate the diaphragm movement. Ultrasound was performed at the end of exhalation (without stimulation) to measure the thickness of the diaphragm, twice per week of participation, and then weekly until RCC discharge. All measurements were taken from muscles on the right-hand side of the participant by the same assessor at all assessment sessions. For the diaphragm, the probe was placed parallel to the anterior axillary line in the intercostal space between the 9th and 10th rib and moved in the cranial and caudal directions until the pleural line was identified. From this point, the probe was moved approximately 1 or 2 intercostal spaces lower to identify the costal diaphragm in the zone of apposition. In all measurements, the probe was placed perpendicular to the skin. We will analyze the diaphragm movement, thickness and the correlation with successful weaning rate.

Flow Chart :

Abbreviation: RCC, respiratory care center; PMV, prolonged mechanical ventilation; NM, neuromuscular; DVT, deep vein thrombosis; CHF, congestive heart failure; BMI, body mass index; TV, tidal volume; MIP, maximal inspiratory pressure; PIP, peak inspiratory pressure; PEEP, positive end-expiratory pressure; UC, usual care; HP, high protein, NMES, neuromuscular electrical stimulation

4.2 Number of Patients

Evaluatable Number: 100

Enrolled Number: 80 (20% dropped out, or failure to finish study)

4.3 Schedule of Activities

Time-Event scheme :

Phase	Screening	Treatment	4±1	6~7	Treatment	8~10	11±1	Treatment	13~14	Treatment	15~17	18±1	Treatment	20~21	Follow-up	22~27	28±1	
Day	0-1	1~3	4±1	6~7	8~10	11±1	13~14	15~17	18±1	20~21	22~27	28±1						
In-hospital visit	X	X	X		X	X		X	X	X	X	X	X	X	X	X	X	
Screening/Administrative/Safety																		
ICF/assent form	X																	
Inclusion/Exclusion criteria	X																	
Medical and surgical history, demographics	X																	
Physical exam	X		X				X				X				X			
Vital signs	X	X	X				X				X			X		X		
Height and body weight	X		X				X				X			X		X		
Pulmonary performance (ventilator)	X		X				X				X			X		X		
Laboratory study	X		X				X				X			X		X		
Barthel index	X																	
Echo for diaphragm evaluation	X		X				X				X			X		X		
Randomization/Administration																		
Randomization	X																	
Administration of high protein diet	X	X	X	X	X	X	X	X	X	X	X	X	X	X				
Administration of core muscle rehabilitation	X	X		X	X		X		X		X		X					
Administration of NMES	X	X		X	X		X		X		X		X					
Efficacy/Safety																		
Weaning profile	X		X				X				X	X	X	X		X		
Creatinine clearance rate	X		X				X				X	X	X	X		X		
Weaning rate													X	X				
Length of mechanical ventilator use													X	X		X		
Length of ICU stay													X	X		X		
Length of hospitalization													X	X		X		
In hospital Mortality													X	X				

5. Study Population

5.1 Inclusion Criteria

The **inclusion criteria** were as follows:

1. age \geq 20 year old
2. using mechanical ventilator for more than 21 days (including patients under tracheostomy or endotracheal tube)
3. stable clinical condition, without using inotropic agent
4. maximal inspiratory pressure (MIP) $<$ 30mmHg
5. under enteral nutrition (EN) via NG tube.

5.2 Exclusion Criteria

The **exclusion criteria** were as follows:

1. Acute infection and sepsis (fever up to 38.5 degree)
2. Severe neuromuscular disease, or uncontrolled epilepsy
3. Bony fracture or DVT history
4. Wound over the abdomen
5. Congestive heart failure with EF $<$ 40% or using pacemaker
6. BMI $>$ 35 kg/M², or severe edema
7. Patients with hepatic failure, rapid progressed malignancy, or pregnancy were also excluded.
8. Under parenteral nutrition (PN)
9. Use pacemaker

5.3 Withdrawal criteria

1. Return to ICU for unstable vital sign or any necessity of surgery.
2. Patient refuse further intervention
3. Physicians judge the patients' condition are not suitable for further intervention.

10. Treatments

6.1.Treatment Administration

1. High protein diet:

The HP groups will maintain unchanged total daily caloric intake and increasing protein content to 1.5g/kg/day. The specific formulas were chosen for their different energy and protein requirement (mainly Nutri-Aid , or NU-PEP HN , according to patients' digestion, and may add Whey-Aid if necessary (above formula are available in CGMH currently)).

We will maintain the nutrition strategies for 21 days according to patients' weaning condition. Protein provision was not reduced in case of renal failure.

2. Core muscle rehabilitation:

Sitting on bedside with or without aids, for 30 minutes, twice per day, 5 days per week, for 3 weeks.

3. Neuromuscular electrical stimulation (NMES):

NMES was applied for 30 min, twice per day, 5 days per week, for 3 weeks, via surface rectangular electrodes. Electrodes were placed on back designed to activate latissimus dorsi and abdominal wall designed to activate the transversus abdominis and internal and external oblique muscles as previously McCaughey et al described ³⁷. Electrical muscle stimulation was performed by using a commercial stimulator (GEMORE, GM300E, Taipei, Taiwan) with biphasic waves at a simulation frequency of 30 Hz and pulse width of 400s, cycling 2s on and 4s off. Electrical muscle stimulation intensity was gradually increased until a visible muscle contraction was observed (median 60 mA [range 50–65 mA].

The subjects in the control group received similar electrode placement and intervention duration, except that the stimulator power was off.

6.2. Concomitant Therapy

Not Applicable

7. Efficacy Assessments

The age, gender, smoking history, diagnosis, length of mechanical ventilator use, APACHE II will be recorded initially.

The pulmonary performance, including tidal volume, maximal inspiratory pressure (MIP), cough function, peak inspiratory pressure (PIP), positive end-expiratory pressure (PEEP), lung compliance, airway resistance, blood gas analysis, Barthel index, serum albumin, creatinine, electrolytes will record before, during (twice per week) and after intervention.

We also follow the outcome of hospitalization, including the weaning rate, mortality, length of mechanical ventilator use, length of ICU stay and total length of hospitalization.

8. Safety Assessments

We will follow serum creatinine level and creatinine clearance rate weekly.

During core muscle rehabilitation and NMES, vital signs (heart rate, blood pressure, respiratory rate) and parameters in ventilator (tidal volume, FiO₂, peak airway pressure) will be monitored.

9. Adverse event reporting

We will report SAEs to the IRB of Chang Gung Medical Foundation according to the Serious Adverse Event Reporting Procedures and Guidelines as posted in the Clinical Trials Resource on the website of Chang Gung Medical Foundation IRB. SAE reports to the IRB should include the following information when calling the Medical Monitor:

- *Date and time of the SAE*
- *Date and time of the SAE report*
- *Name of reporter*
- *Call back phone number*
- *Affiliation/Institution conducting the study*
- *Protocol number*
- *Title of protocol*
- *Description of the SAE, including attribution to drug and expectedness*

9.1 Definitions and reports of Adverse Events

All adverse events that occur after the informed consent is signed (including run-in) must be recorded on the adverse event CRF (paper and/or electronic) whether or not related to study

agent. AE Data Elements including:

- AE reported date
- AE Verbatim Term
- CTCAE Term (v 5.1)
- Event onset date and event ended date
- Severity grade
- Attribution to study agent (relatedness)
- Whether or not the event was reported as a Serious Adverse Event (SAE)
- Action taken with the study agent
- Outcome of the event
- Comments

Identify the adverse event using the NCI Common Terminology Criteria for Adverse Events (CTCAE) version 5.0. The CTCAE provides descriptive terminology and a grading scale for each adverse event listed.

AEs will be assessed according to the CTCAE grade associated with the AE term. AEs that do not have a corresponding CTCAE term will be assessed according to their impact on the participant's ability to perform daily activities as follows:

Grade	Severity	Description
1	Mild	
• Barely noticeable, does not influence functioning• Causing no limitations of usual activities
2	Moderate	
• Makes participant uncomfortable, influences functioning• Causing some limitations of usual activities
3	Severe	
• Severe discomfort, treatment needed• Severe and undesirable, causing inability to carry out usual activities
4	Life threatening	
• Immediate risk of death• Life threatening or disabling
5	Fatal	
• Causes death of the participant

The possibility that the adverse event is related to study drug will be classified as one of the

following: not related, unlikely, possible, probable, definite.

DEFINITION of Serious Adverse Events: ICH Guideline E2A and GCP of Taiwan define serious adverse events as those events, occurring at any dose, which meet any of the following criteria:

- Results in death
- Is life threatening (Note: the term life-threatening refers to an event in which the patient was at risk of death at the time of the event; it does not refer to an event which hypothetically might have caused death if it were more severe).
- Requires inpatient hospitalization or prolongation of existing hospitalization
- Results in persistent or significant disability/incapacity
- Is a congenital abnormality/birth defect
- Events that may not meet these criteria, but which the investigator finds very unusual and/or potentially serious, will also be reported in the same manner.

9.2 Adverse event follow-up

All AEs, including lab abnormalities that in the opinion of the investigator are clinically significant, will be followed according to good medical practices and documented as such. Site staff should send follow-up reports as requested when additional information is available. Additional information should be entered on the IRB of Chang Gung Medical Foundation of SAE form in the appropriate format. Follow-up information should be sent to Chang Gung Medical Foundation IRB as soon as possible according to IRB's Serious Adverse Event Reporting Procedures and Guidelines.

10. Criteria for the termination of the trial

Not applicable.

11. Statistical Considerations

11.1 Sample size Determination

This is an exploratory research, we determine the enrolled number according to the

number of patients admitted to RCC annually.

Ten patients will be assigned to UC group.

Thirty patients will be included in another 3 group.

A total 100 patients will be enrolled.

11.2 Planned Statistical methods of analysis

Categorical variables were expressed as count and percentage. Parametric data were expressed as mean \pm standard deviation (SD). A Student's t-test was used to compare parametric data. Fisher's exact test was used to compare non-parametric data. We used a receiver operating characteristic (ROC) curve to identify the optimal cut-off-value for the maximum multiplication of sensitivity and specificity. Logistic regression was used for multivariate analysis. Kaplan–Meier survival analysis was performed to assess weaning and survival outcomes. Statistical significance was set at a p-value < 0.05 . Statistical analyses were performed using GraphPad Prism version 8 (GraphPad Software, La Jolla, CA, USA) and IBM SPSS Statistics 26 (SPSS, Chicago, IL, USA).

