comparisons, one-way analysis of variance (ANOVA) followed by Dunnett's test, where appropriate, was used to determine the statistical significance of the difference between means. The follow-up parametric data were compared using the paired student's t-test. Non-parametric data were determined by chi-squared tests. Analyses of primary and secondary outcomes are performed with the use of time-to-event methods according to the intention-to-treat principle. All analyses were two-sided, and $p<0.05$ was considered statistically significant. Statistical analyses were performed using Prism version 5 (GraphPad Software Inc., La Jolla, CA, USA).

5. Handling of Missing Data :

Omit the cases with missing data and analyze the remaining data.

2. Introduction and Rationale

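### Tests of means that pool the variance over arms of 10 and 30 hold the 5% level only if the SDs are equal; unequal-variance tests should be prespecified for the continuous outcomes

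*Combined protocol and SAP*

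**What the plan says.** Section 11.2 says of continuous data: "A Student's t-test was used to compare parametric data". It adds: "Statistical significance was set at a p-value < 0.05". The statistical methods paragraph of the synopsis names different tests for the same kind of data: "comparisons, one-way analysis of variance (ANOVA) followed by Dunnett's test, where appropriate". It also says: "All analyses were two-sided".

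Section 11.1 fixes the arms: "Ten patients will be assigned to UC group", "Thirty patients will be included in another 3 group" and "A total 100 patients will be enrolled". Since 10 + 3 × 30 = 100, the thirty is per active arm.

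Neither section names Welch's test or another unequal-variance method, a check of the variances, or a rule for transformation. No SD is given for any outcome.

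**The concern.** Student's t, ANOVA and Dunnett's test all estimate one common variance. With 10 v 30, that estimate comes mostly from the large arm, while the uncertainty in the difference comes mostly from the small one. If usual care is the more variable arm, the standard error is too small and the test rejects too often. If it is the less variable arm, the standard error is too large and power is lost. Usual care is the only control, so every comparison with control carries the imbalance.

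At stake are the p-values for serum albumin, a listed secondary endpoint that section 11.2.1 does not send to a rank test, and for recorded measures such as MIP, tidal volume and lung compliance if they are treated as parametric.

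**Working it through.** **Inputs.** Two-sided 5% (synopsis and 11.2) and arms of 10/30/30/30 (11.1). Assumptions: normal data, active-arm SD of 1, and usual-care SD r from 0.5 to 2.

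**Large-sample check for Student's t.**
- True variance of the difference: V = r²/10 + 1/30.
- Variance that the pooled test uses, on average: E = [(9r² + 29)/38] × (1/10 + 1/30).
- True level ≈ 2 × [1 − Φ(1.96 × √(E/V))].

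Putting the numbers in:
- r = 1: V = E = 0.1333, level 5.0%. The plan's nominal figure is reproduced.
- r = 2: V = 0.4333 and E = (65/38) × 0.1333 = 0.2281. √(E/V) = 0.725, level 15.5%.
- r = 0.5: V = 0.0583 and E = (31.25/38) × 0.1333 = 0.1096. √(E/V) = 1.371, level 0.7%.

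**Simulation with equal means.** There were 400,000 trials per setting. The Dunnett critical value was 2.313 on 96 df, found by simulation. The last digit can move by 0.1 between runs. Entries are true error rates in %.

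| Usual-care SD / active SD | 0.5 | 0.67 | 0.8 | 1 | 1.25 | 1.5 | 2 |
|---|---|---|---|---|---|---|---|
| Student's t, one comparison | 0.9 | 1.8 | 3.0 | 5.0 | 7.9 | 10.7 | 15.4 |
| Welch's t, one comparison | 5.0 | 5.0 | 5.1 | 5.1 | 5.2 | 5.1 | 5.1 |
| ANOVA | 3.3 | 3.5 | 3.9 | 5.0 | 7.2 | 9.8 | 15.5 |
| Dunnett, any of three | 0.3 | 1.1 | 2.3 | 5.0 | 9.4 | 14.0 | 22.1 |
| Dunnett only after significant ANOVA | 0.2 | 0.6 | 1.2 | 2.7 | 5.3 | 8.4 | 14.7 |

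**Dropout.** Section 4.2 has "Enrolled Number: 80 (20% dropped out, or failure to finish study", with its enrolled and evaluable labels reversed against 11.1. Spread evenly, 20% dropout leaves 8/24/24/24. The ranges hardly change: Student's t 1.0% to 15.5%, ungated Dunnett 0.3% to 22.1%.

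**Role of the allocation.** With four arms of 25, Student's t stays at 5.0% to 5.2% over the same ratios. Ungated Dunnett still runs from 2.3% to 9.7%, because it borrows variance from arms outside the comparison. Balance alone would not cure it.

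**Power.** The true difference is 0.8 active-arm SD.
- r = 0.5, one comparison: Student 70%, Welch 89%.
- r = 1, one comparison: Student 57%, Welch 54%.
- r = 1, all three active arms shifted by 0.8, at least one contrast found: ungated Dunnett 62%, Dunnett gated by ANOVA 47%, Welch with Holm 49%.

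**The case against.** The strongest reply is that the documents give no SDs, so nothing shows that this trial's p-values are wrong. That stands. A reader might infer from the unequal arms that the tests do not have their 5% level; the documents support only that they need not have it. At ratios of 0.8 to 1.25, Student's t runs from 3.0% to 7.9%. If an intervention does nothing at all, randomised arms have the same distribution and the level is 5%. Inflation needs equal means with unequal spread.

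Direction matters too. The natural reason for unequal SDs is an intervention that helps only some patients. That would usually widen the active arms, which is the conservative side. The 10.7% to 22% figures need usual care to be 1.5 to 2 times as variable, and the documents give no reason to expect that. Even on the conservative side, it would be wrong to say that the test almost never rejects: that describes the null, and Student's t still finds a difference of 0.8 SD in 70% of trials at ratio 0.5.

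A reader might also take 22% as the error rate of the planned procedure. The synopsis wording can mean Dunnett only after a significant ANOVA, and then the figure at ratio 2 is 14.7%.

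Finally, the reach is narrow, and section 11.1 calls the study exploratory. Both stand, but the plan still sets a 5% threshold, and section 11.2.4 marks results by it.

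**Conclusion.** The point holds as a conditional one. The plan relies on equal variances in a 10 v 30 design without supporting that assumption, and ten patients are too few to check it reliably. Over the assumed SD ratios of 0.5 to 2, the true level of Student's t against usual care is about 0.9% to 15.4%. Dunnett's family-wise error is 0.3% to 22% ungated, or 0.2% to 14.7% gated. With equal SDs, Student's t, ANOVA and ungated Dunnett hold 5%. All figures assume normal data.

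The reach is serum albumin and other continuous measures treated as parametric. No section assigns albumin a test by name, and the synopsis sentence that sends all secondary outcomes to time-to-event methods does not fit it. The documents do not support extending the point to the primary endpoint: weaning rate goes to Kaplan–Meier, categorical or rank methods, the length outcomes to Mann–Whitney, and creatinine to a matched-pairs test. The paired t-test in the synopsis does not pool over arms either. This is a modest, cheap improvement and does not undermine the trial's main result.

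**What to change.** In 11.2, replace Student's t-test by Welch's t-test. In the synopsis, replace pooled ANOVA and Dunnett by Welch comparisons of each active arm with usual care, with a many-to-one multiplicity adjustment such as Holm, so that the two sections agree. State which outcomes this covers, naming serum albumin.

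A check of Welch with Holm (300,000 simulated trials per setting, same model, smallest p compared with 0.05/3) gives a family-wise error of 4.4%, 3.8% and 2.8% at SD ratios 0.5, 1 and 2.

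Two substitutes should be avoided. Dunnett T3 is an all-pairs method; with equal SDs and all arms shifted by 0.8 SD, the chance of finding any of the three contrasts falls from 62% to about 38%. A linear model with HC3 standard errors and no adjustment drops multiplicity control: family-wise error is about 11% with equal SDs.

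The change needs no new data. Its cost, if SDs are equal, is in power:
- One comparison at 0.8 SD: 57% to 54%, about 3 points.
- Any of three contrasts, all arms shifted by 0.8 SD: 62% to 49% against ungated Dunnett, about 13 points; none against Dunnett gated by ANOVA (47%).
- The last comparison depends on the pattern of effects. If only one active arm differs, the same check gives 36% for Welch with Holm against 47% for gated Dunnett, a loss of about 11 points.

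### No between-arm comparison of serum albumin improvement or creatinine clearance is adjusted for the baseline already collected, which costs precision

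*Combined protocol and SAP*

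**What the plan says.** - **Endpoints.** Section 3.2.2 lists "Serum albumin level improvement, Creatinine clearance rate" among the secondary endpoints.
- **Measurement.** Section 7 states: "serum albumin, creatinine, electrolytes will record before, during (twice per week) and after intervention". The schedule in section 4.3 also marks creatinine clearance at screening and at later visits. Both endpoints therefore have a baseline.
- **Between-arm methods.** Section 11.2 says that a Student's "t-test was used to compare parametric data". The Statistical Methods part of the synopsis names one-way ANOVA followed by Dunnett's test. Neither mentions a covariate, and neither says whether the test acts on follow-up values or on changes.
- **Within-patient methods.** The synopsis adds: "The follow-up parametric data were compared using the paired" t-test. Section 11.2.2 assigns serum creatinine and creatinine clearance to a Wilcoxon matched-pairs test of baseline against follow-up.
- **Multivariable methods.** Only logistic regression is named (section 11.2), which does not model a continuous outcome.
- **Arm sizes.** Section 11.1: "Ten patients will be assigned to UC group" and "Thirty patients will be included in another 3 group".

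**The concern.** A paired test asks whether patients within an arm changed. It does not estimate how much more one arm changed than another. That question falls to the t-test or ANOVA, and neither is adjusted for baseline. Each has a weakness. A comparison of follow-up values leaves in the variation that the baseline could explain. A comparison of changes subtracts the whole baseline, which over-corrects whenever the correlation is below 1.

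The design makes precision scarce. Every comparison with usual care rests on 10 patients in that arm, and the sample size was set by admissions, not by power. A free reduction in variance is worth having. Because the plan does not say which quantity is tested, the choice also stays open until the data are seen.

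**Working it through.** **Inputs from the documents**
- Usual care 10. The other arms are read as 30 each, because 10 + 3 × 30 = 100, the stated total (section 11.1).
- Level 0.05 (section 11.2: "Statistical significance was set at a p-value" below 0.05), two-sided (synopsis: "All analyses were two-sided").
- The plan states no power, SD or effect size, so it has no precision figure to reproduce.

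**Assumptions, not in the documents**
- Baseline to follow-up correlation r = 0.3, 0.5, 0.7 or 0.8.
- True difference 0.7 SD, with equal SD at baseline and follow-up.

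**Step 1: variance, in units of the follow-up variance**
- Follow-up values only: 1
- Change score: 2(1 − r)
- ANCOVA: 1 − r²

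The ANCOVA reduction is r² against follow-up values. Against change scores it is 1 − (1 − r²)/[2(1 − r)] = (1 − r)/2.

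| r | Change score | ANCOVA | Reduction v follow-up | Reduction v change |
|---|---|---|---|---|
| 0.3 | 1.40 | 0.91 | 9% | 35% |
| 0.5 | 1.00 | 0.75 | 25% | 25% |
| 0.7 | 0.60 | 0.51 | 49% | 15% |
| 0.8 | 0.40 | 0.36 | 64% | 10% |

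**Step 2: standard error, 10 v 30**

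SE = √[variance × (1/10 + 1/30)]. With variance 1 this is √0.1333 = 0.365 SD. With ANCOVA it is 0.348, 0.316, 0.261 and 0.219 SD at the four correlations.

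**Step 3: power for 0.7 SD, 10 v 30**

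Noncentral t with noncentrality 0.7/SE; 38 degrees of freedom, or 37 for ANCOVA.

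| r | Follow-up only | Change score | ANCOVA |
|---|---|---|---|
| 0.3 | 46% | 35% | 50% |
| 0.5 | 46% | 46% | 58% |
| 0.7 | 46% | 67% | 74% |
| 0.8 | 46% | 84% | 88% |

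The formula ignores the small cost of estimating the slope. Simulation (20,000 runs per row) gives ANCOVA power of 49%, 57%, 73% and 86%, so the formula is about 1 point optimistic.

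**Step 4: other arm sizes at r = 0.5**
- 30 v 30: power rises from 76% to 87% (the two unadjusted analyses coincide at this r).
- 8 v 24, after the 20% dropout in section 4.2: power rises from 38% to 48%.

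**Step 5: chance imbalance**

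The baseline difference for 10 v 30 also has SE 0.365 SD, so it exceeds 0.5 SD in either direction with probability 2[1 − Φ(0.5/0.365)] = 17%. Given a 0.5 SD imbalance, a follow-up comparison shifts by 0.5r (0.25 SD at r = 0.5). A change-score comparison shifts the other way by 0.5(1 − r), also 0.25 SD at r = 0.5. ANCOVA removes this shift.

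**The case against.** **Baseline may already be used.** An endpoint worded as improvement most naturally means change from baseline, so a t-test on it would use the baseline. This stands. A reader might infer that the baseline is ignored altogether, but the documents do not support that. They leave the tested quantity unstated. If it is change and the correlation is 0.7 or 0.8, the gain in power is 7 or 4 points, not 12.

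**Chance imbalance is not bias.** Under valid randomisation it is random error, and the unadjusted standard error already allows for it. This stands. The 17% describes ordinary sampling variation and is no sign of a biased estimate.

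**The paired tests may do no harm.** Suppose every arm changed equally, by 0.5 SD of the differences. A paired t-test would be significant with probability 75.4% at n = 30 and 29.3% at n = 10. A given larger arm would then appear to improve while usual care did not in 0.754 × (1 − 0.293) = 53% of trials. A reader might infer that the plan will present this as a treatment effect. It nowhere says so: the synopsis names ANOVA with Dunnett's test for group comparisons. The figure is a reason to label the paired tests as descriptive, and no more.

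**ANCOVA does not suit every measure.** This stands. Some ventilator readings may not exist after weaning, no measure exists after death, and section 4.3 schedules the Barthel index only at screening. Durations of ventilation and stay have no baseline. Fitting the model only to patients still ventilated would condition on the primary outcome.

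**The stakes are modest.** Section 11.1 calls the trial exploratory, and the primary endpoint, weaning rate, is unaffected. This limits the importance of the point but does not remove it.

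**Conclusion.** The point holds for serum albumin improvement and creatinine clearance. No planned between-arm comparison of either is baseline-adjusted, and the planned paired tests cannot supply one. The consequence is lost precision: for 10 v 30, 9% to 64% of the variance against follow-up values and 35% to 10% against change scores, as the correlation goes from 0.3 to 0.8. In power for a 0.7 SD difference, the gain over the better of the two unadjusted analyses is about 4, 12, 7 and 4 points at r = 0.3, 0.5, 0.7 and 0.8.

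These sizes rest on the assumed correlation and effect, full arm sizes, and a two-arm test at 5% without Dunnett's correction. The correction would change the power levels, but not the variance ratios or the ranking. The figures do not show that the planned estimates are biased. The synopsis sentence sending all secondary outcomes to time-to-event methods is a separate mismatch and carries no weight here.

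**What to change.** In section 11.2 and in the Statistical Methods part of the synopsis:

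1. State that serum albumin and creatinine clearance are compared between arms by ANCOVA at a named end-of-treatment time point, with arm as factor and the patient's own baseline as covariate. A mixed model over the scheduled visits with baseline as covariate is an acceptable alternative.
2. Report adjusted mean differences with 95% confidence intervals, keeping the Dunnett-type comparison with usual care.
3. Label the paired t-test and the Wilcoxon matched-pairs test in section 11.2.2 as within-arm description only.
4. Apply the same model to other repeated measures only where a follow-up value exists whether or not the patient has been weaned.

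The cost is one degree of freedom and a little analysis wording. The baselines are already collected, and SPSS, named in section 11.2, fits the model. The change does not settle how deaths and withdrawals before the time point are handled; that needs its own statement.
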